There will be no active vaccination with Ad26.COV2.S of neonates/infants in this study.

Previously vaccinated participants (Groups 1-3), will receive a single dose of Ad26.COV2.S at 5×10^{10} vp as part of the study. No further vaccinations will be received by these groups during the study.

A booster vaccination with a single dose of Ad26.COV2.S at 5×10^{10} vp will be offered to vaccine naïve consenting participants who have completed pregnancy, are not pregnant again, and haven't received another COVID-19 vaccine (eg, national immunization program). The booster vaccination for vaccine naïve participants at study entry should be administered not earlier than 2 months after the participant's Ad26.COV2.S vaccination in the study. The study duration will not be extended. Dose 2, in this document refers to Booster which is only applicable for Group 4.

Safety assessments include an observation period at the study site after vaccination to monitor for the presence of any severe acute reactions, the recording of any solicited local or systemic adverse events (AEs), unsolicited AEs, serious AEs (SAEs), adverse events of special interest (AESI), pregnancy-related AEs throughout pregnancy, and medically attended adverse events (MAAEs).

Other safety assessments include clinical laboratory assessments, vital signs measurements (pulse/heart rate, supine systolic and diastolic blood pressure, respiratory rate, and body temperature) and physical examinations. In addition, adverse maternal/fetal outcomes, adverse neonate/infant outcomes SAEs (including MIS-C), MAAEs and AEs leading to discontinuation will be recorded.

Active surveillance for COVID-19-like signs and symptoms in participants and neonates/infants will occur, including a COVID-19 surveillance (symptom check) through the participant's electronic diary (electronic clinical outcome assessment [eCOA]). Participants will be asked to confirm whether subjective changes in (postpartum) breast milk production (reduction) have been noticed and report changes in the eCOA diaries. Confirmed SARS-CoV-2 infection will be recorded.

Individuals who do not meet the criteria for participation in this study (screen failure) may be rescreened on 1 occasion only. Participants who are rescreened will be assigned a new participant number, undergo the informed consent process, and then restart a new screening phase.

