5. STATISTICAL ANALYSES

5.1. General Considerations

A baseline (or reference) value will be defined as the value of the last available assessment prior to the first vaccination on Day 1, where Day 1 is the date of first vaccination for adults. A value at birth is baseline value for neonates and the birth date is the neonate reference date. The neonate baseline values for immunogenicity analysis are those from the cord blood sample collected.

Every adult will have a unique subject ID in the ADaM datasets and every neonate will have the same unique subject ID with 'A' added at the end of the ID. Multiple pregnancies [twins or higher order multiples] are excluded from the study but if a participant with multiple pregnancy is inadvertently enrolled, neonates will have the same unique subject ID with 'A', 'B', 'C' and D added at the end of the ID based on the number of neonates.

Unless otherwise specified, continuous variables will be summarized using the following statistics, as appropriate: number of observations, arithmetic mean (mean), standard deviation (SD), standard error (SE), median, minimum, and maximum. Frequencies and percentages (one decimal place) will be generated for categorical variables. Denominator for the percentages is the number of participants in the considered population, and phase (where applicable; incidence per 100 participants/phase).

No formal statistical testing is planned. The safety analysis will be performed on the FAS-A based on actual intervention received and the FAS-NVN, unless otherwise specified. Safety data will be presented by period/phase (as applicable) as well as over the entire study. Immunogenicity results will be conducted on the PPI-A and PPI-NVN and presented per scheduled time point as appropriate. Safety and immunogenicity endpoints will be summarized descriptively by previous vaccination group (as defined in Section 1.2) and overall. All listings will include the previous vaccination group. Vaccination schedule in Group 4 (i.e. vaccine-naive at study entry) will have two components: the Primary Vaccination and the (optional) Booster Vaccination. Listings will be shown per phase and time point, as appropriate.

Participants that took another COVID-19 vaccine during the study are excluded from all safety and immunogenicity analyses from the moment they received the other vaccine. The safety data from those participants after they received the other vaccine will be listed separately.

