5.1.2. Phase Definitions

The phases in the study will be constructed as detailed in Table 3 below.

post partum for adults

e)

f)

d) One minute prior to date and time of

Booster Vaccination (if applicable)

One minute before date and time of another

COVID-19 vaccination outside the study One minute prior to end of the study visit

Table 3: P	hase Defi	nitions			
	Phase		Period		Interval
Phase	#	Period	#	From	То
Screening	1	Screening		Date and time of signing the informed consent form	One minute prior to start of Post-dose 1 period
Post-dose	2	Post-dose 1	1	Date and time of first vaccination	 Minimum of: a) 23:59 at the date of last contact (for early discontinuation) b) 23:59 at the date of data base cut-off date in case of interim analysis c) 23:59 on 28 days after the first vaccination (23:59 of day of vaccination + 28 days) d) One minute prior to date and time of Booster Vaccination e) One minute before date and time of another COVID-19 vaccination outside the study f) One minute prior to neonatal/infant birth or pregnancy termination
Prepartum follow-up 1	3			One minute after Post-dose 1 period end	 Minimum of: a) 23:59 at the date of last contact (for early discontinuation) b) 23:59 at the date of data base cut-off date in case of interim c) One minute prior to 6 months after first vaccination (vaccination date + 6 mths) d) One minute prior to date and time of Booster Vaccination (if applicable) e) One minute before date and time of another COVID-19 vaccination outside the study f) One minute prior to neonatal/infant birth or pregnancy termination
'Postpartum follow-up 1' (adults) and 'Postnatal follow-up 1' (neonates); i.e. PP/PN D1 up to max PP/PN D42	5			Neonatal/infant birth or pregnancy termination	 Minimum of: a) 23:59 at the date of last contact (for early discontinuation) b) 23:59 at the date of database cut-off date in case of interim analysis c) 42 days after the neonate birth date d) One minute prior to date and time of Booster Vaccination (if applicable) e) One minute before date and time of another COVID-19 vaccination outside the study
'Postpartum follow-up 2' (adults); i.e. PP D43 to max PP D366 'Postnatal	6			One minute after postpartum follow-up 1/ Postnatal follow-up 1 period ends	 Minimum of : a) Maximum of 23:59 at the date of last contact (for early discontinuation) and 23:59 at the date of last visit b) 23:59 at the date of data base cut-off date in case of interim analysis c) D183 after birth for neonates and D366

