5.6.2. Laboratory, Vital Signs, and Physical Examinations

Hematology, Chemistry and Urinalysis tests will be performed locally within 72 hours of blood sample collection, according to the Schedules of Activities (CTP 1.3), at Screening (optional, at the discretion of the investigator), at Day 1 (pre-dose): Day 8, Day 15, Day 29 and at delivery (postpartum 1) and postpartum 43 (42 days after delivery). For further details on all laboratory assessments refer to CTP 8.2.3.

Continuous laboratory variables will be summarized using the following statistics, as appropriate: number of observations, arithmetic mean (mean), standard deviation (SD), standard error (SE), median, minimum, and maximum. Frequencies and percentages (one decimal place) will be generated for categorical laboratory variables. Denominator for the percentages is the number of participants in the considered population and phase for a certain regimen (incidence per 100 participants/phase).

For all adult participants, weight and height (and BMI) at baseline will be summarized using descriptive statistics. Physical exam will be summarized and listed for adults. Neonatal physical and birth exam will be summarized and listed for neonates.

Vital signs for adults and neonate/infants including temperature, pulse/heart rate, respiratory rate, blood pressure (adult participants only: systolic and diastolic) and blood oxygen saturation will be summarized over time, using descriptive statistics. Abnormalities emerging after vaccination will be tabulated by worst abnormality grade using the FDA table in Section 6.6.

Temperature will be measured at each scheduled time point and summarized using descriptive statistics. A listing of participants with fever will be provided for adults and neonates. Other vital signs abnormalities will be listed with corresponding grade.

For adult COVID-19 cases, temperature will be summarized over time for the duration of followup of COVID-19 episodes, using descriptive statistics.

All parent(s)/caregiver(s) of neonates/infants with (suspected) COVID-19 should measure blood oxygen saturation and body temperature.

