An abnormality (toxicity grade or abnormality based on normal ranges) will be considered as emerging in a particular period if it is worse than the baseline value. If the baseline is missing, the abnormality is always considered emerging. A shift from 'abnormally low' at baseline to 'abnormally high' post baseline (or vice versa) is also emerging. In case a laboratory test result is censored (no numeric value is available, but only a verbatim term) then a numeric value will be imputed by a value exceeding the cut-off value with one unit. (<x: subtract 1 unit from x, >x: add 1 unit to x: e.g., <3.45 is imputed with 3.44, <90 with 89 and >101 with 102).

In case no toxicity grades are defined for a test, the abnormalities (above/below normal range) will be used. In determining toxicity grades, the following rules are applied:

- worst grades/abnormalities are determined over the whole observational period for each trial period separately, including all post-baseline measurements of that period.
- The abnormalities 'abnormally low' and 'abnormally high' are considered equally important, i.e. if a participant has as well an abnormally low as an abnormally high value post-baseline, both abnormalities are shown in the tables. (This means that the sum of the percentages can be more than 100%).
- Note: as the grading scale for some parameters in the grading table has some gaps (zones where no toxicity grade definition exists), results falling in these zones will be allocated to the adjacent worst-case grade. For example if a laboratory result falls within the 'grey area' between the ranges for 'Grade 1' and 'Grade 2' in the FDA table, then this result would be allocated to 'Grade 2' (the adjacent worst-case grade).
- If a value falls within the grading as specified in the grading FDA table but using the local laboratory it falls within normal limits, the value is considered as normal. For example, if the local lab classifies a result as 'normal' within their prespecified limits, then the value can indeed be considered normal even when according to the FDA table it would be 'Grade 1'.

For the grades, no distinction will be made between test results of samples obtained under fasting and under non-fasting conditions.

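### Emerging laboratory and vital-sign abnormalities after the booster are judged against a pregnancy value taken before dose 1 (SAP 5.1 and 5.6.2)

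*SAP*

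**What the plan says.** - **One adult baseline.** Section 5.1 defines it as "the value of the last available assessment prior to the first vaccination on Day 1". Dose 1 is given between Week 16 and Week 38 of gestation (section 1.2), so this is a pregnancy value.
- **Emergence rule.** Under section 5.6.2 an abnormality "will be considered as emerging in a particular period if it is worse than the baseline value".
- **Per-period tabulation.** In the same section, "worst grades/abnormalities are determined over the whole observational period for each trial period separately". For vital signs, "Abnormalities emerging after vaccination will be tabulated by worst abnormality grade using the FDA table in Section 6.6". Section 5.1 brings unscheduled results into the worst grade. Table 3 makes Post-dose 2, Booster follow-up 1 and Booster follow-up 2 periods or phases in their own right.
- **Who is boosted, and when.** Section 1.2 offers the booster to vaccine-naïve, consenting "participants who have completed pregnancy, are not pregnant again", and "not earlier than 2 months after the participant's Ad26.COV2.S vaccination in the study".
- **Laboratory visits.** After Day 29, section 5.6.2 lists only samples "at delivery (postpartum 1) and postpartum 43 (42 days after delivery"). No laboratory visit is tied to the booster.
- **Booster reference elsewhere.** Section 5.7.1.5.1 calculates fold change from the pre-booster value for neutralization titers and carries the same rules over to S-ELISA and MSD 4-plex. Section 5.1 also gives post-booster safety assessments a day number relative to the booster. No section does the same for the baseline value of laboratory or vital-sign data.

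**The concern.** A table of abnormalities emerging after a dose should show what is new since that dose. Here the reference for the booster periods lies on the other side of delivery, so two errors are possible.

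- **False attribution.** An abnormality absent at dose 1 that appears at delivery and is still present after the booster counts as emerging post-booster, although it came first.
- **Masking.** An abnormality present at dose 1, resolved before the booster and back at the same grade afterwards is not worse than baseline, so it is not shown as emerging.

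The error can therefore go either way. Section 6.6 adds a direct case: one female hemoglobin grade is defined by the fall from baseline, so it inherits the dose-1 reference.

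**Working it through.** The SAP states no figure on this point. The check is whether the rules reach real data, and when.

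**Step 1: the rule, case by case.** Same parameter, same direction:

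| At dose 1 | Last value before booster | After booster | Current rule | Against pre-booster value |
|---|---|---|---|---|
| Normal | Grade 2 (e.g. at delivery) | Grade 2 | Emerging post-booster | Not emerging |
| Grade 1 | Normal | Grade 1 | Not emerging | Emerging |

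In the first row the abnormality is also counted in Postpartum follow-up 1, because worst grades are taken per period.

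**Step 2: can a scheduled laboratory visit fall after the booster?** Inputs:
- dose 1 at gestational week *w*, from 16 to 38 (section 1.2);
- earliest booster 61 days after dose 1, taking the 2 months of section 1.2 as more than 60 days, the cut-off in section 5.1.3;
- delivery at Week 40 (280 days), an assumption, with Week 37 (259 days) to show the range;
- last scheduled laboratory visit 42 days after delivery (section 5.6.2).

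Earliest booster, in days after delivery = max(0, 7*w* + 61 − delivery day). Birth is postpartum Day 1 in the SAP, so the postpartum day is this figure plus 1.

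| Delivery | *w* | 7*w* + 61 − delivery day | Days after delivery | Postpartum day |
|---|---|---|---|---|
| Week 40 | 31 | 217 + 61 − 280 = −2 | 0 | 1 |
| Week 40 | 34 | 238 + 61 − 280 = 19 | 19 | 20 |
| Week 40 | 36 | 252 + 61 − 280 = 33 | 33 | 34 |
| Week 40 | 38 | 266 + 61 − 280 = 47 | 47 | 48 |
| Week 37 | 31 | 217 + 61 − 259 = 19 | 19 | 20 |
| Week 37 | 34 | 238 + 61 − 259 = 40 | 40 | 41 |

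A zero is the arithmetic limit; it does not say that boosters are given then. The result reaches 42 days at *w* = (280 + 42 − 61)/7 = 37.3 for delivery at Week 40, and at (259 + 42 − 61)/7 = 34.3 for Week 37. Below those weeks a booster before the postpartum-43 visit is possible.

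**Step 3: which period takes that sample?** Table 3 ends Postpartum follow-up 1 at the booster, and Post-dose 2 runs for 28 days. Since 43 − 28 = 15, the sample falls in Post-dose 2 if the booster was on postpartum Day 15 to 42, and in Booster follow-up 1 if earlier.

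**Step 4: age of the reference.** At the booster the dose-1 value is at least 61 days old. With dose 1 at Week 16 it is at least (37 − 16) × 7 = 147 days old for delivery at Week 37, or (40 − 16) × 7 = 168 days for Week 40.

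**Step 5: effect on a percentage.** The SAP does not say how many women are boosted. The Group 4 target was at least 25. If 25 were boosted (an assumption), one misclassified woman moves a percentage by 1/25 = 4 points, and by more if fewer were boosted.

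**The case against.** The strongest reply is that little of the booster safety assessment depends on this rule, and that holds. The endpoints in sections 1.1 and 5.4.1 are solicited and unsolicited AEs, SAEs, AESIs, MAAEs and AEs leading to discontinuation. Section 5.6.1.4 assigns solicited events to the post-dose period and other AEs by start date and time. Fever is summarized by highest observed grade. None of these uses the baseline value. A reader might infer that booster safety as a whole is judged on the wrong baseline; the SAP does not support that.

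A reader might also take the Table 3 clause "One minute prior to date and time of Booster Vaccination (if applicable") under Postpartum follow-up 1 as evidence that boosters are given in the first 42 days. It is not. Prepartum follow-up 1 carries the same clause and Post-dose 1 a near-identical one, and no booster can occur in either under section 1.2. The clause is generic. Step 2 shows that overlap is possible, not that it is common.

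Third, a pre-booster reference is not clean. The SAP lists no dedicated pre-booster safety sample, so for an early booster the last laboratory value may be the delivery sample. A delivery abnormality used as reference could hide a new one of the same or lower grade. This stands, and it is the reason to show both references.

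Other limits also hold. A shift from low to high, or the reverse, counts as emerging, so masking needs the same direction and no worse grade. Results within local normal limits are treated as normal. Vital-sign abnormalities are also listed with their grade. None of this changes what the period tables would show in the two cases of Step 1.

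**Conclusion.** The point holds within a narrow scope. Sections 5.1 and 5.6.2 together state a rule, rather than merely leaving a detail open: post-booster emergence of laboratory and vital-sign abnormalities, and the hemoglobin-change grade, refer to a pregnancy value taken before dose 1. The SAP re-references the booster for immunogenicity and for relative day but not here.

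Those affected are Group 4 booster recipients with a postpartum-43 or unscheduled laboratory value, or vital signs, after the booster. Their number is not given, and the timing in Step 2 rests on assumed delivery weeks and a 61-day minimum interval. All the tables are descriptive and no hypothesis is tested. Priority: minor.

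**What to change.** Add to sections 5.1 and 5.6.2:

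*For Post-dose 2 and Booster follow-up 1 and 2, emergence of laboratory and vital-sign abnormalities and hemoglobin change are derived against the last available assessment before the booster; results against the pre-dose-1 baseline are also shown.*

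This costs one derived baseline flag and one extra table column, and needs no new data. A footnote should say when the pre-booster value is the delivery sample, so that the two columns can be read together.

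### When Group 4 women are boosted within a postpartum phase, their per-phase SAE, AESI and discontinuation percentages rest on shorter follow-up than those of Groups 1-3, and no person-time is shown

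*SAP*

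**What the plan says.** Section 5.1 sets the denominator: "Denominator for the percentages is the number of participants in the considered population, and phase (where applicable; incidence per 100 participants/phase". It also sets the layout: "Safety and immunogenicity endpoints will be summarized descriptively by previous vaccination group (as defined in Section 1.2) and overall". Safety is to be shown by period or phase where applicable, and over the entire study.

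Table 3 ends adult Postpartum follow-up 1 and 2 at the earliest of several dates. One of them, in both phases, is "One minute prior to date and time of Booster Vaccination (if applicable". The full span of the second phase is "i.e. PP D43 to max PP D366".

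Section 1.2 confines the booster to women who were vaccine naïve at entry (Group 4). It "will be offered to vaccine naïve consenting participants who have completed pregnancy, are not pregnant again", provided they have had no other COVID-19 vaccine, and it "should be administered not earlier than 2 months after the participant's Ad26.COV2.S vaccination in the study". No latest date and no expected uptake are given. Section 5.1 describes the Group 4 schedule as "the Primary Vaccination and the (optional) Booster Vaccination". Of Groups 1-3, Section 1.2 says: "No further vaccinations will be received by these groups during the study".

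No person-time or exposure-adjusted rate is planned. Section 5.2 tabulates participants per phase, and Section 5.7.6 summarises days from first vaccination to booster.

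**The concern.** The booster stop can shorten the postpartum phases of Group 4 only, and a head count does not register the shortening. A Group 4 woman boosted on PP D60 contributes 17 days to Postpartum follow-up 2. A woman in Groups 1-3 can contribute 324. Each counts as one.

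The groups are displayed side by side. A lower Group 4 percentage for SAEs, AESIs or discontinuations in these phases could be read as better tolerability in vaccine-naïve women when it only reflects less observation. The study is descriptive, so the displayed percentages are the result; no later model corrects them.

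The whole-study tables do not settle the first-dose question either. In boosted women, the Table 4 Primary Vaccination Period is cut at the booster, and the Entire Study interval includes time after a second dose.

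**Working it through.** **Figures in the SAP.** The SAP states no postpartum event rate to reproduce. Its zero-event limits in Section 3 (8.8%, 6%, 3%, 1.5% for n = 40, 60, 120, 240) follow from 1 − 0.025^(1/n), which gives 8.81%, 5.96%, 3.03% and 1.53%. They are not used below.

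**Inputs from the SAP.** Postpartum follow-up 2 lasts at most 366 − 43 + 1 = 324 days. A woman boosted on PP day b (b > 43) keeps b − 43 days. Planned minimum sizes are 40 in each of Groups 1-3 and 25 in Group 4, so Group 4 is 25/145 = 17%. An equal split of 240 gives 60/240 = 25%. Enrolment has since ceased, so these are planned weights only.

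**Assumptions, not in the SAP.** The hazard is constant and equal in all women, with risk p = 5% over 324 days. A share s of Group 4 is boosted on day b. Nobody else leaves the phase early.

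**Per woman.** Risk in the phase = 1 − 0.95^((b − 43)/324).
- b = 60: 17 days kept, 95% of the phase unobserved, risk 0.27%
- b = 120: 77 days kept, 76% unobserved, risk 1.21%
- b = 183: 140 days kept, 57% unobserved, risk 2.19%

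**Per group.** Group 4 % = s × [1 − 0.95^((b − 43)/324)] + (1 − s) × 5%. For s = 0.5 and b = 90: 0.5 × 0.74 + 0.5 × 5.00 = 2.87%. Overall = (25 × 2.87 + 120 × 5.00)/145 = 4.63%, or 0.25 × 2.87 + 0.75 × 5.00 = 4.47%.

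| Boosters in Group 4 | Group 4 % | Groups 1-3 % | Overall % (25/145) | Overall % (60/240) |
|---|---|---|---|---|
| None | 5.00 | 5.00 | 5.00 | 5.00 |
| Half at D275 | 4.30 | 5.00 | 4.88 | 4.83 |
| Half at D183 | 3.60 | 5.00 | 4.76 | 4.65 |
| Half at D90 | 2.87 | 5.00 | 4.63 | 4.47 |
| All at D90 | 0.74 | 5.00 | 4.27 | 3.94 |
| All at D61 | 0.28 | 5.00 | 4.19 | 3.82 |

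Relative to the full window, Group 4 shows between 6% and 100% of the true figure, and overall about 76% to 100%. These ratios barely change for p = 2% or 10%.

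**With person-time.** The daily hazard is −ln(0.95)/324 = 0.000158, or 0.058 per person-year. With half of Group 4 boosted at D90, events divided by person-time to first event or end of phase give 0.058 per person-year in Group 4 and in Groups 1-3. Under this model the gap of 2.9% against 5.0% is entirely an effect of follow-up.

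**MAAE window.** Section 5.6.1.3 tabulates MAAEs to 6 months (taken as 183 days) after each vaccination. Assuming delivery at 40 weeks, the window from the first dose ends near PP D15, D99 and D169 for vaccination at week 16, 28 and 38 (for example 183 − 24 × 7 = 15). The 324-day arithmetic therefore does not carry over to MAAEs.

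**The case against.** The strongest reply is that ending a phase at the booster is sound. It attributes events to the dose that preceded them. Later events move to Post-dose 2 and Booster follow-up 1 and 2; they are not lost. The Group 4 figure is a valid pre-booster proportion. This stands, and it is why the phases should stay. It does not make proportions over unequal windows comparable.

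SAEs, AESIs and discontinuations are defined over the whole study (Section 5.3.1) and tabulated that way (Section 5.6.1.3), uncut at the booster. The note under Table 3 makes AE display by phase optional. The primary analysis stops at the Day 42 postpartum visit (Section 5.8.2), so Postpartum follow-up 2 matters only at the final analysis. A reader might infer that the primary safety endpoints themselves are biased; the documents do not support that.

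A reader might also infer that all AE percentages are affected. General unsolicited AEs are tabulated only for 28 days after a vaccination, and MAAEs have their own window.

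Nor do women boosted by PP D42 dilute Postpartum follow-up 2. They have no time in that phase and should not be in a denominator defined by phase. They do shorten Postpartum follow-up 1.

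The numbers are small. With half boosted at D90, the shortfall is (5.00 − 2.87)% × 25 = 0.5 of a woman, or 1.3 among 60. The exact 95% interval for 1/25 is 0.1% to 20.4%, so chance will often swamp the effect. Existing outputs also give part of the picture (participants per phase, days to booster).

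Person-time rates have their own weakness. If half of the phase's hazard fell in D43-D89 (assumption), women boosted at D90 would show 0.5 × 324/47 = 3.4 times the average rate of unboosted women, about 0.20 against 0.058 per person-year, purely from timing. The fix must state this limit.

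**Conclusion.** The point holds in a conditional form. If Group 4 women are boosted within a postpartum phase, the per-phase SAE, AESI and discontinuation percentages, and part of the MAAE rows, compare shortened windows with windows that can run to PP D366. The effect against a full window is downward in Group 4 and slight in the overall column.

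Under the 5% constant-hazard assumption with half of Group 4 boosted at D90, the display would be 2.9% against 5.0%, with about 4.5-4.6% overall. Uptake and timing drive the size, and the SAP gives neither.

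A reader might conclude that Group 4 rates are too low by construction. They are not: the booster is optional, unboosted women are not cut at a booster, and with no boosters the bias is zero. Groups 1-3 do not all reach PP D366 either, since discontinuation, end of study or another COVID-19 vaccine also ends their phases. What remains is a display that can mislead about a group contrast, with no planned output showing the unequal follow-up.

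**What to change.** Keep the phases and the head-count percentages, and add the following:

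- Total and median person-time per phase, by group and overall, in the header of each postpartum safety table.
- For SAEs, AESIs and AEs leading to discontinuation in the postpartum phases, exposure-adjusted incidence: participants with an event per 100 person-months, time counted to first event or end of phase, with an exact Poisson 95% CI. Cumulative incidence censored at the booster is an acceptable alternative and does not need a constant hazard.
- For MAAEs, person-time counted only inside the 6-month reporting window. Otherwise time when MAAEs are no longer tabulated would inflate the denominator.
- A footnote that Group 4 head-count percentages in these phases reflect shorter observation in boosted women, and that the rates assume a roughly constant hazard.

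No formal group comparison should be added; the study is descriptive and has no hypothesis. The cost is slightly longer outputs. All dates needed are already derived for Table 3, and no endpoint or study procedure changes.
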